#### 1. STUDY SUMMARY

Extensor Carpi Radialis Brevis (ECRB) tendinopathy, also known as lateral epicondylitis or tennis elbow, is the most prevalent elbow soft tissue injury and affects 1-3% of the population. Repetitive overloading of the tendon and ligaments in the elbow lead to microtraumas, causing abnormal angiofibroblastic remodeling and increased pain. Microtearing occurs most commonly at the origin of the extensor carpi radialis brevis (ECRB) tendon. The main symptoms include a loss of grip strength, a burning sensation near the ECRB origin site, and pain during daily activities such as grasping objects or shaking hands. Both conditions present a significant injury and treatment burden on the population and effective treatment and pain management approaches with minimal side effects are needed.

Novel nonsurgical treatment approaches for ECRB tendinopathy include platelet-rich plasma (PRP) injections and stem cell therapy. Ultrasound-guided PRP and adipose-derived stem cells (ASCs) injections have shown to be an effective treatment option for patients with chronic ECRB tendinopathy.

The proposed study seeks to assess the effect of non-compressive semiconductor embedded arm sleeves in combination with PRP + ASC injections, throughout a 6-month rehabilitation course for patients with ECRB tendinopathy. Outcome measures will be collected at standardized intervals to evaluate and compare treatment groups.

# 2. BACKGROUND

Unlike compression products, the semiconductor embedded fabric increases blood circulation through activation of the embedded elements with heat of the body and releases mid and far infrared waves as well as negative ions. Both infrared waves and negative ions are biologically active and mediate inflammatory and pain pathways in the body. The technology has also been shown to:

- Increase blood flow and velocity
- Reduce osteoarthritis pain
- Reduce effusion post total knee arthroplasty
- Improve chondrogenic differentiation in vitro
- Improve muscle recovery
- Increase circulation by up to 22% at rest
- Improve functional outcomes

The benefits of the Infrared Wave and Negative Ion therapy include:

- Inhibition of Cox-2 and Prostaglandins in the lipopolysaccharide (LPS)-moderated pain pathway
- Up-regulation of heat shock protein
- Mediated Nitric oxide production
- Increased activity of voltage-gated ion channels
- Increased activity of mechanosensitive ion channels

- Polarization of cell surface membranes
- Protecting muscle damage
- Scavenging of Reactive Oxygen Species (ROS)
- Improved thermoregulation

To date, studies have shown that the semiconductor embedded fabric increase circulation by up to 22% at rest, and have shown powerful results in reducing inflammation, swelling, improving range of motion in the knee post-surgery, and providing pain relief to the joints.

The semiconductor embedded fabric emits mid-level and far infrared waves and negative ions. Delivery of infrared waves and negative ions to the tissue increases circulation of both blood and lymph, facilitates the anti-inflammatory nitric oxide (NO) cascade by accelerating the binding of calcium (Ca2+) to calmodulin (CaM). NO provides several healing factors to the body, increasing blood and lymphatic flow. Additionally, NO down-regulates interleukin-1 beta (IL1 $\beta$ ) and inducible nitric oxide synthase (iNOS) in certain cell types, which leads to reduced cyclooxygenase-2 (COX-2) and prostaglandins – molecules responsible for causing inflammation and pain. Unlike other systemic COX-2 inhibitors such as nonsteroidal anti-inflammatory drugs (NSAIDs), targeted infrared and negative ion therapy stimulate localized reaction pathways, thereby reducing pain and inflammation.

This study seeks to identify patient reported and clinically measured outcomes for pain management and elbow function with application of semiconductor embedded fabric combined with PRP+ASC injections in the affected area.

#### 3. OBJECTIVES

- 1. Determine the effect of the semiconductor embedded arm sleeves on patient reported and clinically measured outcomes in patients with ECRB tendinopathy.
- 2. Evaluate the change in symptoms in patients following treatment with the semiconductor embedded arm sleeves.

### 4. HYPOTHESIS

Subjects who are assigned and compliant to wearing the semiconductor embedded arm sleeve will experience improved outcomes in symptoms, pain management, and elbow function throughout the course of the study compared to the patients assigned to wear and compliant with wearing the placebo sleeves.

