#### **Primary Endpoint**

Completion of 8 weeks wearing the semiconductor embedded arm sleeves with at least 80 subjects.

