## **Primary Outcome**

Improvement in patient function in patients using the semiconductor embedded sleeve compared to placebo as measured by PRTEE.

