## **Secondary Outcomes**

- 1. Reduction in pain as determined by Numeric Pain Rating Scale or Visual Analog Scale (VAS) compared to placebo group.
- 2. Improvement in patient function as determined by Patient Specific elbow PROMIS score (Disabilities of the Arm, Shoulder, and Hand (DASH) and Patient-Rated Tennis Elbow Evaluation (PRTEE)) and the patient specific functional score compared to control and placebo groups.
- 3. Reduction in symptom severity upon physical examination and improvement in grip strength compared to placebo group.

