#### 5. STUDY DESIGN

The study will be prospective, randomized, and double-blinded with at least 80 subjects that will be recruited by the principal investigator (PI). Patients meeting enrollment criteria will undergo an informed consent discussion prior to any study activity.

Subjects meeting enrollment criteria and consenting to participation will undergo a 6- month trial.

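### The only efficacy hypothesis compares compliant wearers with compliant wearers, a contrast formed after randomisation and at odds with the protocol's own aim, objectives and secondary outcomes

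*Protocol*

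**What the plan says.** Protocol section 4 (Hypothesis) conditions both arms on compliance. On the active side, "Subjects who are assigned and compliant to wearing the semiconductor embedded arm sleeve will experience improved outcomes in symptoms". The comparison is made "throughout the course of the study compared to the patients assigned to wear and compliant with wearing the placebo sleeves".

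Other parts of the protocol describe the comparison without that condition:

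- Section 1 (Study Summary): "Outcome measures will be collected at standardized intervals to evaluate and compare treatment groups".
- Section 3 (Objectives), first objective: "Determine the effect of the semiconductor embedded arm sleeves on patient reported and clinically measured outcomes in patients with ECRB tendinopathy".
- Secondary Outcomes, third item: "Reduction in symptom severity upon physical examination and improvement in grip strength compared to placebo group".

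The Primary Outcome lies in between: "Improvement in patient function in patients using the semiconductor embedded sleeve compared to placebo as measured by PRTEE". Its word *using* could mean assigned to or actually wearing, and it does not qualify the placebo side.

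On timing, section 5 (Study groups) has the sleeve assigned at random and then instructs subjects to wear it at least 12 hours daily for the whole study. Wear is recorded in a self-reported device usage log (Description of Measures). Table 1 marks this log only in its daily column, and the footnote ends required daily reporting at week 8.

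**The concern.** Randomisation makes the two sleeve groups comparable at the moment of assignment. Whether a subject then complies is observed later, and it may depend on the sleeve, on early symptoms and on prognosis. Compliant active subjects and compliant placebo subjects are therefore two selected subsets, and nothing in the design makes them comparable. If the arms differ in the rate of compliance, or in the reasons for it, a comparison of these subsets can show a difference when the sleeve does nothing, or hide a real effect.

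A reader also cannot tell from the protocol which question the trial is meant to answer. An analysis that follows section 4 takes on the selected contrast. One that follows the objectives and secondary outcomes leaves the stated hypothesis untested.

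A secondary issue is that the hypothesis claims benefit over the whole study, while the record that would show compliance is required for only the first part of it.

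**Working it through.** **1. Which statements carry a compliance condition**

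| Protocol section | Comparison described | Compliance condition |
|---|---|---|
| 1. Study Summary | treatment groups | none |
| 3. Objectives | effect of the sleeve in patients with the condition | none |
| 4. Hypothesis | active versus placebo | both arms |
| Primary Outcome | active versus placebo | ambiguous (*using*) |
| Secondary Outcomes | active versus placebo group | none |

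The Primary and Secondary Endpoint paragraphs also speak of wearing the sleeve (for example "Completion of 8 weeks wearing the semiconductor embedded arm sleeves with at least 80 subjects"). They count subjects who complete a period of wear and do not define a between-arm comparison.

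**2. Coverage of the usage log** (6 months taken as 26 weeks)

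- Primary endpoint period: 8/8 weeks = 100%.
- Whole study: 8/26 = 31% covered; 18/26 = 69% with no required record.
- Patient-reported outcome timepoints after enrolment in Table 1: 2, 4 and 8 weeks, 3 and 6 months. Three of five fall within the log period and two after it.

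**3. Possible size of the bias (illustration; every input is assumed)**

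Suppose the sleeve has no effect and only compliers are compared. Let c be the compliant fraction in an arm and r the correlation between the tendency to comply and the outcome. With z = Φ⁻¹(1 − c), the mean shift among compliers is r·φ(z)/c in SD units, and the bias is the difference in this shift between arms.

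φ(z)/c = 0.350 at c = 0.8, 0.497 at c = 0.7 and 0.644 at c = 0.6.

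| Compliance in the two arms | r | Bias (SD) |
|---|---|---|
| 80% and 80% | 0.3 in both | 0.3 × (0.350 − 0.350) = 0 |
| 70% and 80% | 0.3 in both | 0.3 × (0.497 − 0.350) = 0.044 |
| 60% and 80% | 0.3 in both | 0.3 × (0.644 − 0.350) = 0.088 |
| 80% and 80% | 0.3 in one arm, 0 in the other | 0.3 × 0.350 = 0.105 |
| 60% and 80% | 0.5 in both | 0.5 × (0.644 − 0.350) = 0.147 |
| 80% and 80% | 0.5 in one arm, 0 in the other | 0.5 × 0.350 = 0.175 |

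The sign depends on which arm is the more selected, so either sleeve could be favoured.

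**4. Effect on error rates and precision (illustration)**

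The protocol gives no design inputs for its 80 subjects, so that figure cannot be reproduced; it is not in dispute here. Assume 40 per arm and a two-sided 5% test. With 60% and 80% compliance, the type I error of the complier comparison is 6.2% at r = 0.3 and 8.5% at r = 0.5.

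The difference detectable with 80% power is (1.96 + 0.84) × √(2/n). With all 40 per arm it is 0.63 SD. Among compliers only it is 0.70 SD at 80% compliance (n = 32) and 0.81 SD at 60% (n = 24).

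**The case against.** The strongest reply is that section 4 is a hypothesis and not an analysis rule. No part of the protocol removes non-compliers. Analysis sets are commonly left to the statistical analysis plan, which is not at hand and could analyse as randomised in line with the objectives. This stands, and it makes the harm conditional. It does not remove the inconsistency, because such an analysis would still leave the protocol's stated hypothesis untested.

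A second reply is that the design limits the bias: "The study will be prospective, randomized, and double-blinded with at least 80 subjects", with a sham sleeve and the same compliance condition in both arms. This also stands. Under symmetric compliance the bias is zero, and blinding makes the larger values in the illustration less likely. A model with selection in opposite directions gives more (0.35 SD at r = 0.5 and 80% compliance in each arm), but the protocol offers no basis for it.

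A third reply is that benefit when a wearable is actually worn is a legitimate question, given the mechanism described in section 2. That is a reason to keep the comparison as supportive. It is not a reason to make it the only hypothesis.

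Three stronger readings are tempting, and the protocol does not support them:

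- That section 4 alone uses wear-based language. The Primary Outcome and both endpoint paragraphs use it too, though none of them sets a compliance criterion for a comparison.
- That the log identifies compliers at week 8. It records usage, but compliance is nowhere defined, and the 12-hour instruction is not stated as a threshold.
- That compliance at 6 months is unknowable. It cannot be established from the required log. Logging beyond week 8 is not prohibited, and subjects are contacted at 3 and 6 months.

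**Conclusion.** The concern holds as an inconsistency that should be corrected. Section 4 states a complier-versus-complier contrast that randomisation does not protect, and the study aim, objectives and secondary outcomes do not share that condition. The importance is minor to moderate. Any bias arises only if section 4 is followed, and neither its size nor its direction can be derived from the document. The illustrated range, 0 to about 0.17 SD, rests wholly on assumed compliance rates and correlations and is modest in most cases.

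A reader might infer that the trial will exclude non-compliers or that its result will be biased; the protocol supports neither. The gap in the usage log after week 8 matters only for a compliant-wearer analysis. Once the hypothesis is stated by assigned sleeve, the gap no longer affects the main comparison.

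**What to change.** - **Section 4:** restate the hypothesis as all randomised subjects compared by assigned sleeve, semiconductor versus placebo, whatever their wear time.
- **Primary Outcome:** replace *using* with *assigned to*.
- **Compliant-wearer comparison, if kept:** label it supportive and define compliance in advance from the device usage log. Limit it to the 8-week timepoint, or to compliance measured up to week 8, unless the log is continued.

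The first two changes are wording only and need no extra subjects or visits. The price is that the as-assigned effect may be smaller than the effect among compliant wearers. If non-compliers gain nothing and compliance is equal in both arms (assumed), it is c times as large: 0.9, 0.8 or 0.6 times at 90%, 80% or 60% compliance. Continuing the log past week 8 is optional and would add reporting burden for subjects.

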#### **Primary Endpoint**

Completion of 8 weeks wearing the semiconductor embedded arm sleeves with at least 80 subjects.

## **Secondary Endpoint**

Completion of 6 months wearing the semiconductor embedded arm sleeves with at least 80 subjects. Additional subjects may be required to enroll in the study to achieve a total of 80 subjects who complete all outcome measures for 6 months.

## **Primary Outcome**

Improvement in patient function in patients using the semiconductor embedded sleeve compared to placebo as measured by PRTEE.

## **Secondary Outcomes**

- 1. Reduction in pain as determined by Numeric Pain Rating Scale or Visual Analog Scale (VAS) compared to placebo group.
- 2. Improvement in patient function as determined by Patient Specific elbow PROMIS score (Disabilities of the Arm, Shoulder, and Hand (DASH) and Patient-Rated Tennis Elbow Evaluation (PRTEE)) and the patient specific functional score compared to control and placebo groups.
- 3. Reduction in symptom severity upon physical examination and improvement in grip strength compared to placebo group.

#### 5. STUDY DESIGN

The study will be prospective, randomized, and double-blinded with at least 80 subjects that will be recruited by the principal investigator (PI). Patients meeting enrollment criteria will undergo an informed consent discussion prior to any study activity.

Subjects meeting enrollment criteria and consenting to participation will undergo a 6- month trial.

### Study groups:

- a. Among participants who opt out of receiving PRP+ASC injections as part of their routine medical care:
  - i. One group will receive active therapy (semiconductor embedded arm sleeve) "Incrediwear only"
  - ii. One group will receive placebo therapy (arm sleeve absent of semiconductor thread) "Sham Incrediwear"
- b. Among participants who choose to receive PRP+ASC injections as part of their routine medical care:
  - i. One group will receive active therapy with SOC PRP+ASC injections (active semiconductor embedded arm sleeves after they have received PRP+ ASC injections as part of their routine care) "Incrediwear with SOC PRP+ASC injections"
  - ii. One group will receive placebo therapy with SOC PRP+ASC injections (arm sleeve absent of semiconductor fabric after they have received PRP+ASC injections as part of their routine care) "Sham Incrediwear with SOC PRP+ASC injections"

Subjects will determine whether they would like to receive Standard of Care (SOC) PRP+ASC injections. Then, the subjects will be randomly assigned to the study group in which they will receive a real or sham semiconductor embedded sleeve. The subjects will be instructed to wear the sleeve for a minimum of 12 hours per day, including overnight, for the entire duration of the study.

Patients will determine whether to receive PRP+ASC injections independent of their participation in this research study. Then, they will be assigned to a study group and will either receive a real or sham sleeve. Study groups will be blinded, randomly assigned, and block randomized based on the severity of ECRB tendinopathy (lateral epicondylitis). Severity of ECRB tendinopathy will be ranked as mild, moderate or severe as follows:

Mild – tendinopathy with no visible tearing of ECRB tendon.

Moderate – visible partial tear of ECRB tendon, less than 50%

Severe – greater than 50% tear, but less than 100% tear of ECRB tendon.

All subjects participating in the study will also be assigned to the standard physical therapy routine, without direct interventions including dry needling, Graston blading, laser therapy or iontophoresis.

#### **Inclusion Criteria**

- 1. Patients diagnosed with ECRB tendinopathy as determined by radiographic assessment or ultrasound imaging.
- 2. Patients age 18-65
- 3. Patients who are willing and able to adhere to follow-up schedule and protocol guidelines.
- 4. Patients who are willing and able to sign corresponding research subject consent form.

## **Exclusion Criteria**

- 1. Patient has a history of neurological conditions, including multiple sclerosis or Parkinson's disease
- 2. Patient has severe medical condition, including recent myocardial infarction, unstable angina, heart failure, severe anemia
- 3. Patient has had prior surgical treatment of the elbow in the last 5 years or injection treatment(s) in the last 2 years
- 4. Patient has complete tear of ECRB tendon or other surgical indication
- 5. Patient has chronic pain conditions unrelated to elbow condition
- 6. Patient has auto-immune or auto-inflammatory diseases
- 7. Patient has used tobacco within the last 90 days
- 8. Patient is not within the ages of 18-65
- 9. Patient has a history of metabolic disorders
- 10. Patient has an active infection (local or systemic)
- 11. Patient is unwilling or unable to sign the corresponding research subject consent form

12. Patient meets any other criteria or has any other condition that, in the opinion of the investigator, would prevent them from completing the study or that, in the opinion of the investigator, would confound study results.

## **Study Measures**

Subjects will complete a variety of repeated subjective and objective measures throughout the course of the study. A schedule of study-related events can be found in Table 1.

TABLE 1	Enrollment Visit	2-Week Follow-Up Phone Call	4-Week Follow- Up Phone Call	8-Week Follow- Up Visit	3 Month Follow-Up Phone Call	6 Month Follow-Up Visit	*Daily Reported
Enrollment Screening	X						
Informed Consent Discussions	X						
PROM Scores 	X	X	X	X	X	X	
Numeric Visual Analog Scale 	X	X	X	X	X	X	X
Patient Specific Functional Score 	X	X	X	X	X	X	
PFG Measurement (Grip Strength Test) 	X			X		X	
Device Usage Log							X
Medications Log							X

\*Daily reported measures will only be required up to the 8-week timepoint.

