## **Description of Measures**

*Enrollment Screening:* Patient demographic information, past medical history, weight, history of pain, prior treatments, and any secondary diagnoses will be recorded to ensure the patient is a candidate for the trial.

Informed Consent Discussion: Doctor or study staff will explain the research, go through corresponding research subject consent form, and answer patient questions.

(Disabilities of the Arm, Shoulder, and Hand (DASH) and Patient-Rated Tennis Elbow Evaluation (PRTEE)): Patient will report the difficulty in performing various activities, elbow-related quality of life, and the level of pain experienced in the previous week.

Visual Analog Scale  $(VAS)^{20}$ : Patient will self-report pain level in the shoulder on a 0-10 scale at the same time each day for consistency.

Patient Specific Functional Score: Patient will identify and score up to three important activities they are unable to do or have difficulty doing due to elbow injury.

Hand Grip Strength Test: Doctor or study staff will measure the patient's grip strength with a dynamometer.

Device Usage Log: Patient will self-report device usage, including time of therapy initiation, time of therapy completion, and device location.

Medications Log: Patient will self-report medication intake, including type and quantity.

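### The only record of sleeve wear stops being required at week 8, so the secondary endpoint of 6 months' wear in at least 80 subjects cannot be established from the schedule

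*Protocol*

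**What the plan says.** The Secondary Endpoint opens with a wear target: "Completion of 6 months wearing the semiconductor embedded arm sleeves with at least 80 subjects". Its next sentence allows further enrolment to "achieve a total of 80 subjects who complete all outcome measures for 6 months", which is a target for completed assessments.

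Under Study groups, subjects are "instructed to wear the sleeve for a minimum of 12 hours per day, including overnight, for the entire duration of the study". That duration is 6 months: the Study Summary describes sleeve use "throughout a 6-month rehabilitation course for patients with ECRB tendinopathy", and the Study Design section says that those "consenting to participation will undergo a 6- month trial".

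The Description of Measures gives one wear instrument: "Device Usage Log: Patient will self-report device usage, including time of therapy initiation, time of therapy completion, and device location". In Table 1 this log is marked only in the daily column, and the footnote to that column reads "Daily reported measures will only be required up to the 8-week timepoint".

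**The concern.** An endpoint defined by 6 months of wear needs some record of wear over those 6 months. Under the schedule, a site that follows the Protocol exactly stops collecting wear data at week 8 and never asks about it again.

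Two things are at stake. First, the trial could not show from its scheduled data how many subjects met its own 6-month wear target. Second, the Hypothesis concerns subjects who are both assigned to and compliant with their sleeve, but it sets no period over which compliance is judged. Any compliance-based reading of the 3- and 6-month results would rest on wear in weeks 0 to 8 alone. If the 6-month comparison showed no difference, the trial could not distinguish a sleeve that does not work from one that subjects stopped wearing. This cannot be left to a statistical analysis plan, because the gap is in what is collected.

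**Working it through.** The Protocol gives no figure for wear coverage, so there is none to reproduce. The check reads Table 1 against the endpoint and then counts the uncovered time.

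**Table 1, the six scheduled contacts (enrollment, 2 weeks, 4 weeks, 8 weeks, 3 months, 6 months)**

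| Measure | Contacts marked | Daily column (required to week 8) |
|---|---|---|
| "Numeric Visual Analog Scale" | 6 of 6 | yes |
| Device Usage Log | 0 of 6 | yes |

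The pain scale is a useful control. It is also a daily item, but because it is marked at every contact it continues after the daily column ends. The Device Usage Log does not.

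**Contacts after week 8**
- 3-month call: patient-reported outcome scores, pain scale, patient-specific functional score (3 measures, none of them wear).
- 6-month visit: the same three plus grip strength (4 measures, none of them wear).

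**Share of the wear period without a required record.** Inputs: log required to week 8 (Table 1 footnote); trial length 6 months (Study Design). Assumption: 6 months = 26 weeks.
- Covered: 8 × 7 = 56 days. Total: 26 × 7 = 182 days.
- Not covered: 26 − 8 = 18 weeks, or 182 − 56 = 126 days.
- Shares: 126/182 = 69% not covered; 56/182 = 31% covered.
- With 6 calendar months of 181 to 184 days: (181 − 56)/181 = 125/181 = 69%, to (184 − 56)/184 = 128/184 = 70%.

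**Recall windows if a question were added at the existing contacts.** Assumption: month 3 = 13 weeks = 91 days.
- Week 8 to month 3: 91 − 56 = 35 days (33 to 36 if 3 calendar months are 89 to 92 days).
- Month 3 to month 6: 182 − 91 = 91 days (89 to 92 by calendar).
- Check: 35 + 91 = 126 days, which matches the gap above.

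**The case against.** The strongest reply is that the wear sentence is shorthand for finishing the study. Read literally, it needs at least 80 subjects in the active sleeve, while the Study Design section plans at least 80 subjects in all, divided between active and sham. The second sentence of the Secondary Endpoint speaks of completing outcome measures, and the scheduled contacts can count that. This stands as a reading of intent. But completing questionnaires shows retention, not wear. If retention is what is meant, the first sentence is wrong as written and needs changing.

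Other points limit the weight of the concern:
- The endpoints are completion targets. The efficacy outcomes are listed separately, and wear is not among them.
- Ending a daily diary at the primary time point limits burden, although the Protocol does not give that reason.
- The footnote says what is required and does not forbid later logging. The section on IRB review, ethics and informed consent names questionnaires and case report forms whose content is not shown. Wear could be captured there, but nothing in the Protocol commits anyone to doing so.
- The Secondary Endpoint sets no threshold for having completed wear, so a recall question alone would not say who completed it. The wear instruction of at least 12 hours per day gives a yardstick to compare answers with, but the gap in definition is real and favours the rewording option.
- The null-result argument matters only if wear fell after week 8, and nothing in the Protocol indicates whether or how far it would.

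**Conclusion.** The concern holds. The Secondary Endpoint, the wear instruction and the Table 1 footnote do not fit together: wear is an endpoint for 6 months, but its only record is required for 8 weeks. About 69% of the wear period (126 of 182 days; 69% to 70% under calendar counting) has no required or scheduled wear record. The percentage assumes that 6 months is about 26 weeks; the inconsistency itself does not depend on that assumption.

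The figure measures missing wear records. It does not measure bias or lost outcome data. What is lost is the 6-month wear count and part of the interpretation of the later results. The log covers the period of the 8-week primary endpoint, and the blinded comparison by assigned sleeve at 3 and 6 months stays valid. The change should be made, because the loss cannot be repaired after follow-up and the remedy is small.

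**What to change.** Either of two changes reconciles the text.

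1. Add a short device-use item to Table 1 at the 3-month call and the 6-month visit, asking for typical hours per day and days per week since the last contact. Table 1 already continues the pain scale at these contacts. The cost is one or two questions at contacts that will take place anyway. Recall over about 35 and 91 days is coarser than a daily log, and there is slight extra burden. If this route is taken, also state what counts as having completed wear.
2. Reword the Secondary Endpoint so that 6-month completion is defined by the outcome measures, as its second sentence already suggests, and state that compliance is assessed from the log for weeks 0 to 8 only. This costs a wording change, and it accepts that later results cannot be interpreted by actual wear after week 8.
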